6.27 Adverse Event (AE) and Serious Adverse Event (SAE)

6.27.1 Definitions

Term	Definition
Adverse Event (AE)	Any untoward medical occurrence, unintended disease or injury, or untoward clinical signs (including abnormal laboratory findings) in subjects, users or other persons, whether or not related to the medical device used in the investigation*. This definition includes events related to the procedures involved.
Adverse Device Effect (ADE)	Adverse event related to the use of medical device used in the investigation*. 
 • This definition includes adverse events resulting from insufficient or inadequate instructions for use, deployment, implantation, installation, or operation, or any malfunction of the investigational medical device. • This definition includes any event resulting from use error or from intentional misuse of the investigational medical device.
Serious Adverse Event (SAE)	A SAE** is an adverse event that: 
 • results in death • is life-threatening • requires inpatient hospitalisation or prolongation of existing hospitalisation • results in persistent or significant disability/incapacity • is a congenital anomaly/birth defect • has led to a important medical event that may have jeopardised the subject or may have required an intervention to prevent one of the above characteristics/ consequences. These can include complaints that might have led to a medical occurrence if 
 ○ suitable action had not been taken or ○ intervention had not been made or ○ if circumstances had been less fortunate. 
NOTE: Planned hospitalization for a pre-existing condition, or a procedure required by the CIP, without serious deterioration in health, is not considered a serious adverse event.

Serious Adverse Device Effect (SADE)	Adverse device effect that has resulted in any of the consequences characteristic of a serious Adverse Event
Unanticipated Serious	Serious adverse device effect which by its nature, incidence, severity or

Adverse Device Effect (USADE)	outcome has not been identified in the current version of the risk analysis report
Device deficiency	Inadequacy of a medical device with respect to its identity, quality, durability, reliability, safety or performance NOTE Device deficiencies include malfunctions, use errors, and inadequate labelling.

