6.27.2 Handling and reporting of AEs

Subjects will be carefully monitored during the investigation for possible AEs and appropriate treatment of the subject will be initiated.

Any AE observed will be fully investigated by the investigator and documented in the case report form (CRF) including assessment of severity (mild, moderate or severe) and relationship to the medical device.

6.27.3 Reporting of SAEs and device deficiency that could have lead to a SAE

An investigator should report within 24 hours, after being aware of the event, an SAE or a device deficiency that could have lead to a SAE. The report should be sent as an e-mail attachment to Cochlear Bone Anchored Solutions AB. Instructions and contact information is available on the SAE form.

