3.3 Safety Variables

3.3.1 Adverse Events

Treatment emergent adverse events will be presented. Treatment emergent is defined as an event happening at or after surgery. Three predefined AE categories (Magnetic retention difficulties, Pressure related skin complications, Pain/Discomfort) will be used, and if other is checked those will be MedDRA (version 18.0) coded.

- Adverse Event (AE) is all reported events
- Adverse Device Effect (ADE) is events that is Related to the device (Probably) or Related to the procedure (Probably)
- Serious Adverse Event (SAE) is events that has been marked as Serious
- Serious Adverse Device Effect (SADE) is events that has been marked as Serious and also marked as Related to the device (Probably) or Related to the procedure (Probably)

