4.11 Safety Analyses

4.11.1 Adverse Events

Only treatment-emergent AEs will be included in the summaries for safety population.

Protocol:

Post-market clinical follow-up of a magnetic bone conduction implant

Protocol No:

CBAS5477

Version:

1.0

Page 15 of
18

A summary of subjects reporting at least one of the following AEs will be presented in an overview table:

- Any AE
- Any SAE
- Any Adverse Device Effect (ADE)
- Any Serious Adverse Device Effect (SADE)

Summaries per predefined AE, SOC and PT presenting n (%) of AEs and n (%) of subjects with at least one AE will be provided for:

- All AE
- All SAE
- All Adverse Device Effect (ADE)
- All Serious Adverse Device Effect (SADE)

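### SAP 3.3.1 counts ADEs and SADEs only at the grade 'Probably', a threshold the protocol does not set; if the CRF has other positive grades, those events are left out of the ADE and SADE tables

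*SAP*

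**What the plan says.** SAP 3.3.1 sets out how each class of event is counted. The widest class has no condition on causality: "Adverse Event (AE) is all reported events". The device-effect class does: "Adverse Device Effect (ADE) is events that is Related to the device (Probably) or Related to the procedure (Probably". A SADE is an event "marked as Serious and also marked as Related to the device (Probably) or Related to the procedure (Probably", so it carries the same condition plus seriousness. No other relatedness grade is named anywhere in the SAP.

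Protocol 6.27.1 defines an ADE as "Adverse event related to the use of medical device used in the investigation" and a SADE as "Adverse device effect that has resulted in any of the consequences characteristic of a serious Adverse Event". Neither definition mentions a degree of certainty.

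Protocol 6.27.2 says what the investigator records for each event: "assessment of severity (mild, moderate or severe) and relationship to the medical device". It spells out the severity levels but not the relationship levels.

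SAP 4.11.1 uses the ADE and SADE classes in the overview table and in the summaries by predefined category, system organ class and preferred term. SAP section 6 states that the analyses do not depart from the protocol.

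**The concern.** The protocol asks whether an event is related; the SAP asks whether it carries one particular label. The two agree only if that label is the sole positive answer on the CRF, and a reader cannot tell whether it is.

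The rule is also odd as a cut-off. It names a single grade and does not say 'at least'. On a scale with several positive grades, a programmer following the text would drop the less certain events and also any graded as more certain than probable. A 'probable or higher' threshold could be defended, but one that excludes the most certain cases could not.

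Evaluating mid- to long-term safety is one of the two stated rationales (Protocol 1.2). With one device group and no control (SAP 1.2 and 1.3), the investigator's causality judgement is the main means by which the AE tables separate device effects from background events. The ADE and SADE definition therefore deserves to be unambiguous.

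**Working it through.** The plan gives no figure to reproduce: there are no event counts and no relatedness scale. The check compares the texts and then bounds the possible effect.

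**Step 1: compare the definitions.**
- *AE:* all reported events in the SAP. Relatedness plays no part.
- *ADE:* the protocol requires relation to use of the device, with no threshold. The SAP requires 'Probably' related to the device or 'Probably' related to the procedure.
- *SADE:* the protocol requires an ADE with serious consequences. The SAP requires the same 'Probably' condition and a serious mark.
- *Declared change:* none in SAP section 6.

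On certainty the SAP is narrower than the protocol. On scope it is not, because it expressly admits procedure-related events, which the protocol's ADE definition does not name in those terms.

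**Step 2: ask whether the scale is likely to be graded.** The SAP presents its two-way items as Yes/No (soft tissue thinning, bone polishing, device deficiency, soft tissue status, implant loss), and seriousness is simply a mark. Only relatedness carries a word of degree in brackets. That suggests a graded item but does not prove it, since the bracketed word could be the printed label of the only positive box.

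**Step 3: apply the SAP rule to possible CRF scales.** These scales are assumptions; the documents give none.
- *Not related / probably:* every related event is counted and nothing is lost.
- *Not related / possibly / probably:* events graded possibly are left out.
- *Not related / possibly / probably / definitely:* events graded possibly and events graded definitely are left out.

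**Step 4: bound the effect.** Let N be the number of events with a positive grade for the device or the procedure. Let M be the number of those graded 'Probably' for neither, and let s = M / N.
- Count under the SAP rule: N − M = N × (1 − s).
- Relative understatement: [N − N × (1 − s)] / N = s.
- One positive option on the CRF: M = 0, so s = 0.
- Several positive options: M can be anything from 0 to N, so s lies between 0 and 100%.

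The same formula holds for SADEs, with N and M restricted to serious events. The two shares need not be equal.

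**Step 5: see which outputs are affected.** Those that depend on the definition are Tables 14.3.1.1 (its ADE and SADE rows), 14.3.1.3 and 14.3.1.5. Tables 14.3.1.2 (all AEs) and 14.3.1.4 (all SAEs) do not depend on it. Nor do the by-visit summaries of pain, numbness, device deficiency and soft tissue status (SAP 4.11.2), or the implant and magnet loss analyses (SAP 4.11.3).

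**The case against.** The strongest reply is that no loss has been shown. The CRF is not among the documents, and no text shows that a second positive grade exists. The SAP wording reads much like a tick-box label, and since no analyst would mean to exclude the most certain cases, 'Probably' may be the top or only positive option. This stands: a reader might infer that events are in fact dropped, but the documents support that only conditionally.

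A reader might also infer that the plan hides events or makes the device look safer overall. That is not supported. Retention difficulties, pressure-related skin complications and pain or discomfort are predefined AE categories, summarised for all AEs and all SAEs whatever the causality grade. The certainty condition alone can only lower the ADE and SADE counts, but the procedure limb can raise them relative to the protocol's definition, so the net direction against the protocol is not established. Nor do the documents rank the ADE tables as the main safety output. The reporting of SAEs under Protocol 6.27.3 does not use the SAP rule.

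Finally, Protocol 8.10 leaves analysis detail to the SAP, and Protocol 6.27.1 does not say how certainty grades translate into 'related'. The SAP may fill that gap. It should then do so openly: state the scale, and declare any threshold that narrows the protocol's definition. Section 6 does the opposite by declaring that nothing changed.

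**Conclusion.** The point holds in conditional form. Two things are certain from the text: the SAP restricts ADE and SADE to one certainty grade where the protocol sets none, and the difference is undeclared while the scale is given nowhere. The numerical consequence is unknown. It is an understatement of s, between 0 and 100% of events related to the device or procedure, and exactly 0 if the CRF has one positive option. It concerns the attribution of events in the ADE and SADE summaries; every event remains visible in the AE or SAE tables. The primary efficacy analysis is untouched. The change is worth making because the sentence cannot be programmed safely without knowing the CRF, and because the correction does no harm if 'Probably' proves to be the only positive option.

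**What to change.** In SAP 3.3.1:
- Define an ADE as an event with any positive relatedness grade, to the device or to the procedure. That means 'possibly' or more certain, including any grade above 'probably'. Define a SADE as the same with a serious mark.
- List the CRF grades that qualify. Do not count 'unlikely' or 'not related'.
- Keep the existing procedure limb, so that correcting the certainty rule does not silently change the scope.
- If wanted, add a row for 'Probably or higher' to the ADE and SADE tables.

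If the sponsor prefers a higher threshold, keep it but declare it in SAP section 6 as a departure from Protocol 6.27.1.

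The cost is a few lines of SAP text and one derivation. No new data are needed if the grades are already on the CRF. The downside is that ADE and SADE counts may look slightly less favourable.

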3.3.2 Pain and numbness

- Pain/discomfort (w 6, w 12, m 6, m 12 and m 24)
 - No discomfort and/or pain.
 - Slight discomfort and/or pain
 - Discomfort and/or pain
 - Excessive discomfort and/or pain
- Numbness (pin) (d 10, w 4, w 6, w 12, m 6, m 12 and m 24)
 - No numbness
 - Numbness within 2 cm from the implant
 - Numbness within and beyond 2 cm from the implant
- Numbness (cotton swab) (d 10, w 4, w 6, w 12, m 6, m 12 and m 24)
 - No numbness
 - Numbness within 2 cm from the implant
 - Numbness within and beyond 2 cm from the implant

3.3.3 Device deficiency and Soft tissue status

Device deficiency will be collected at d 0, d 10, w 4, w 6, w 12, m 6, m 12 and m 24.

- Has any device deficiency occurred?
 - Yes
 - No

Soft tissue status will be collected at d 10, w 4, w 6, w 12, m 6, m 12 and m 24.

- Any signs of infection, inflammation, skin necrosis and/or scar hypertrophy?
 - Yes
 - No

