6.18 Baha sound processor fitting on SP Magnet

The Baha sound processor that was selected during the initial sound processor selection at Visit 1 (see Section 6.9) will be fitted with the SP Magnet to the implant at Visit 4 (i.e. 4 weeks after surgery). A suitable SP Magnet shall be selected as described in Section 6.19. Sound processor fitting shall be performed in accordance with the information in the Fitting Guide (Baha Fitting Software 4.0 or later generation). If the wound is not considered sufficiently healed, as judged by the surgeon/surgical nurse, the installation shall be delayed to a scheduled subsequent visit or extra visit, when the site is considered sufficiently healed.

The subject will receive a User Guide, which contains important information regarding the device.

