1.2.1 Flowchart

Procedures and timing	Visit 1 Softband test	Visit 2 Surgery	Visit 3 Suture removal	Visit 4 Fitting	Visit 5	Visit 6	Visit 7	Visit 8 *	Visit 9 *
Day/Week/Month ¹	Pre-op	D 0	D 10	W 4	W 6	W 12	M 6	M 12	M 24
Time window			± 5d	± 1w	± 1w	± 2w	± 4w	± 4w	± 4w
Demographics	X								
Medical history	X								
Nicotine use	X								
Audiogram ²	X								X
Eligibility criteria	X								
Informed consent	X								
Soft tissue thickness	X or X								
Health Utility Index (HUI) ³	X ⁴						X		X
Abbreviated Profile of Hearing Aid Benefit (APHAB) ³	X ^{4,5}						X ⁶		X ⁶
The Speech, Spatial and Qualities of Hearing Scale (SSQ) ³	X ^{4,5}						X ⁶		X ⁶
BC Direct using BFS	X ⁷			X ⁸					X ⁹
Selection of sound processor	X								
Change of sound processor				X ⁹	X ⁹	X ⁹	X ⁹	X ⁹	X ⁹
Fitting of sound processor	X ⁷			X ⁸					X ⁹
Fine tuning of sound processor					X ⁹	X ⁹	X ⁹	X ⁹	X ⁹
Free field thresholds	X ^{5,7}			X ⁸			X ⁸	X ⁸	X ⁸
Speech recognition in noise	X ^{5,7}			X ⁸			X ⁸	X ⁸	X ⁸
Speech recognition in quiet	X ^{5,7}			X ⁸			X ⁸	X ⁸	X ⁸
Home test of sound processor on Softband	X →								
Surgery		X							
Surgery time		X							
Soft tissue thinning		X							
Bone polishing/removal		X							
Implant stability quotient		X							
Suture removal (if applicable)			X						
SP Magnet selection				X					
Magnetic retention force				X	X	X	X	X	X
Change of SP Magnet					X ⁹	X ⁹	X ⁹	X ⁹	X ⁹
Questions regarding: • Daily use of sound processor • Magnet retention • Change of soft pad					X	X	X	X	X
Pain/discomfort					X	X	X	X	X
Numbness			X	X	X	X	X	X	X
Soft tissue status			X	X	X	X	X	X	X
Loss/removal of Implant or Implant Magnet			X	X	X	X	X	X	X

STATISTISKA KONSULTGRUPPEN		Statistical Analysis Plan	
Protocol: Post-market clinical follow-up of a magnetic bone conduction implant		Protocol No: CBAS5477	
		Version: 1.0	Page 7 of 18

Device deficiency		X	X	X	X	X	X	X	X
Adverse Events		X	X	X	X	X	X	X	X
Concomitant medication/treatment	X	X	X	X	X	X	X	X	X
Extra visit									
Extra visit									

¹ The time between visits was calculated from Visit 2 (time 0); ² Only if the last audiogram that was performed on the subject was older than 6 months; ³ To be completed by the subject; ⁴ Before Softband test; ⁵ Unaided; ⁶ Aided; ⁷ With sound processor on Softband; ⁸ With Baha Attract System; ⁹ If needed; * Visit 8 and 9 are not included in the sixth months analysis

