4 STATISTICAL METHODOLOGY

4.1 General Methodology

Since all included subjects will have measurements of the primary and important secondary efficacy variables for unaided hearing, with the sound processor on a Softband and with the Baha Attract System, all statistical analyses will be paired. All statistical analyses will be non-parametric. In order to choose the most powerful test, the Fisher's non-parametric permutation test for paired observations will be used for all paired analyses of continuous variables. The permutation tests use the measured values and not only the ranks in the calculations. For paired analysis of dichotomous and ordered categorical variables the Sign test will be used.

The analyses will be performed in the following priority:

1. Baha Attract System vs. Unaided
2. Baha Attract System vs. the sound processor on a Baha Softband

In addition to the change variables the distribution of all efficacy variables will be presented by visit, where applicable.

The main efficacy analysis will be performed on the ITT population and complementary efficacy analyses will be performed on the PP population. The main analysis will be performed after the 6 month visit. A complementary analysis will be performed 18 months after the main analysis (24-month visit). All significance tests will be two-sided and performed at the 5% significance level.

Imputation of missing values will be performed for all efficacy variables. No imputation of baseline values will be made. Imputations will be made according to the following rules:

1. If a value is missing at the end of a patient last observation will be carried forward
2. If a missing value is occurring between two time points with values, an interpolation will be made for continuous variables and for categorical variables the value from the previous visit will be carried forward.

The distribution of continuous variables as well as change in continuous variables will be given as n, mean, SD, SEM, Median, Min and Max and the distribution of dichotomous and categorical variables will be given as number and percentages.

Adverse Events, Device deficiencies, Surgical variables, Demographics Baseline, Questions, Magnetic force and Magnet strength variables will only be analysed descriptively.

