4.11.2 Pain/discomfort, Numbness, Device deficiency and Soft tissue status

Pain/discomfort, Numbness, Device deficiency and Soft tissue status will be presented by visit.

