Table 14.2.18	The Speech, Spatial and Qualities of Hearing Scale (SSQ) (Conductive/Mixed patients ITT Population)
Table 14.2.7.1	Surgery (ITT population)
Table 14.2.7.2	Surgery (PP population)
Table 14.2.8.1	Sound processor magnet, total and by magnet strength (ITT population)
Table 14.2.8.2	Sound processor magnet, total and by magnet strength (PP population)
Table 14.2.9.1	Usage (ITT population)
Table 14.2.9.2	Usage (PP population)
Table 14.3.1.1	Summary of Adverse Events (Safety Population)
Table 14.3.1.2	Adverse Events (AE), by Predefined AEs, System Organ Class and Preferred Term (Safety Population)
Table 14.3.1.3	Adverse Device Events (ADE), by Predefined AEs, System Organ Class and Preferred Term (Safety Population)
Table 14.3.1.4	Serious Adverse Events (SAE), by Predefined SAEs, System Organ Class and Preferred Term (Safety Population)
Table 14.3.1.5	Serious Adverse Device Events (SADE), by Predefined SADEs, System Organ Class and Preferred Term (Safety Population)
Table 14.3.2	Pain and Numbness (Safety Population)
Table 14.3.3	Device deficiency (Safety Population)
Table 14.3.4	Soft tissue status (Safety Population)
Table 14.3.5	Implant loss/removal and magnet loss/removal (Safety Population)

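### Device deficiency is tabulated only as a percentage Yes per visit, with no stated look-back and unequal intervals, so visits are not comparable and no subject total is given

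*SAP*

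**What the plan says.** SAP 3.3.3 gives the item as "Has any device deficiency occurred", answered Yes or No, and sets the timing: "Device deficiency will be collected at d 0, d 10, w 4, w 6, w 12, m 6, m 12 and m 24". It states no look-back period and lists no date of deficiency.

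SAP 4.11.2 sets the display: "Pain/discomfort, Numbness, Device deficiency and Soft tissue status will be presented by visit". Under SAP 4.1, "the distribution of dichotomous and categorical variables will be given as number and percentages", and device deficiencies are among the variables with no testing: "Adverse Events, Device deficiencies, Surgical variables, Demographics Baseline, Questions, Magnetic force and Magnet strength variables will only be analysed descriptively". The one planned output is Table 14.3.3, on the Safety population. Listings are left outside the SAP (7.3).

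Other items are handled differently:

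- Protocol 6.21 gives a recall period of a week or a month for daily use, loss of retention and Soft pad changes.
- SAP 3.2.2 converts Soft pad changes to a weekly rate, because the recall periods differ between visits.
- SAP 3.3.4 records dates of implant and implant magnet loss or removal, and SAP 4.11.3 plans tables and Kaplan-Meier figures for them.

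**The concern.** Pain, numbness and soft tissue signs can be read as the subject's state at the visit, so a percentage per visit suits them. A device deficiency is an event that falls somewhere in an interval. Its percentage depends on how long the interval is as well as on how often deficiencies occur. When the intervals differ several-fold and the look-back is not stated, the row of percentages in Table 14.3.3 mixes the two.

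Collecting device deficiencies is a secondary objective in both documents. The rationale in Protocol 1.2 is mid- to long-term safety, and the definition in Protocol 6.26 includes durability and reliability, which are properties over time. A reader of the 24-month report would naturally scan the row for a trend and look for the number of subjects affected. The table supports neither use as planned.

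**Working it through.** The documents give no deficiency rate or percentage, so there is no planned figure to reproduce. All rates below are assumptions chosen for illustration.

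**Step 1: interval lengths.** The flowchart times visits from surgery. Taking days 0, 10, 28, 42, 84, 183, 365 and 730, the intervals closed by each visit are:

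| Visit | d 10 | w 4 | w 6 | w 12 | m 6 | m 12 | m 24 |
|---|---|---|---|---|---|---|---|
| Days | 10 | 18 | 14 | 42 | 99 | 182 | 365 |

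The last interval is 365/14 = 26 times the week 6 interval. It holds 365/730 = 50% of follow-up, against 14/730 = 1.9% for week 6. The visit windows add variation. With ±1 week at both w 4 and w 6, the interval closed at w 6 can last from 35 − 35 = 0 to 49 − 21 = 28 days.

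**Step 2: 'since the last visit', constant rate.** P(Yes) = 1 − exp(−rate × days/30.4).

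| Assumed rate | w 6 | w 12 | m 6 | m 12 | m 24 |
|---|---|---|---|---|---|
| 1% per month | 0.5% | 1.4% | 3.2% | 5.8% | 11.3% |

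For example, at w 6: 1 − exp(−0.01 × 14/30.4) = 0.46%. At m 24: 1 − exp(−0.01 × 365/30.4) = 11.3%. At 0.5% per month, w 6 and m 24 read 0.2% and 5.8%. At 2% they read 0.9% and 21.3%. The underlying rate is flat in every case.

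In 52 subjects, the 1% case is about 52 × 0.0046 = 0.2 subjects at w 6 and 52 × 0.113 = 5.9 at m 24.

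**Step 3: 'since the last visit', falling rate.** Assume a Weibull time to deficiency with shape 0.3 and 10% cumulative at 24 months, so H(t) = −ln(0.9) × (t/730.5)^0.3. The interval percentage is 1 − exp(−[H(end) − H(start)]).

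| Visit | d 10 | w 4 | w 6 | w 12 | m 6 | m 12 | m 24 |
|---|---|---|---|---|---|---|---|
| % Yes | 2.87 | 1.05 | 0.51 | 1.03 | 1.43 | 1.59 | 1.96 |

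From w 12 to m 24 the tabulated percentage nearly doubles. Per day it falls from 1.03/42 = 0.0245% to 1.96/365 = 0.0054%, about 4.5 times lower. More simply, an equal low percentage at m 12 and m 24 implies that the rate has about halved, because the interval has doubled (182 to 365 days).

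**Step 4: 'ever'.** P(Yes) = 1 − exp(−rate × days since surgery/30.4). At 1% per month this is 1.4% at w 6 (42 days) and 21.3% at m 24 (730 days). The same data would give a different row, and the SAP does not say which row is meant.

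**Step 5: subject total.** Under 'since the last visit', adding the visit counts counts a subject with two positive visits twice. Under 'ever', the m 24 column leaves out subjects who have withdrawn. Neither reading yields the number of subjects with at least one deficiency.

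**The case against.** The item is descriptive, the objective is only to collect deficiencies, and no claim about deterioration is planned. Much of what matters for safety also appears elsewhere. A malfunction that leads to an adverse event counts as an adverse device effect and is summarised by events and by subjects (SAP 4.11.1). Magnetic retention difficulty is a predefined category, and implant and magnet loss have dated displays. What is left is mainly deficiencies without harm. The look-back may also be printed on the CRF or in its instructions, which are not among the documents. All of this stands, and it keeps the severity low. It does not make the by-visit percentages comparable or supply a subject total.

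Some stronger readings are tempting but not supported:

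- *The percentage must rise over follow-up.* This follows only under 'ever', and only among subjects still followed. Under 'since the last visit' it needs a constant or slowly falling rate, and early clustering can flatten or reverse it (Step 3). The intervals do not lengthen at every step either: 18 days is followed by 14.
- *The table cannot show a change in rate.* If the look-back is 'since the last visit', a reader can divide by the nominal interval, and a marked early cluster would show in its own short column. The table merely does not do this, and nominal intervals ignore the windows.
- *The d 0 and d 10 columns are empty of meaning because the processor is fitted only at Visit 4.* Those visits can still capture deficiencies of implanted parts and surgical instruments.
- *Event counts, an exact-date Kaplan-Meier curve and risk time by component are owed.* SAP 3.3.3 lists no event count, deficiency date or failed component, so those outputs may not be obtainable.

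**Conclusion.** The point holds and is minor. Table 14.3.3 presents an occurrence item, with undefined look-back, over intervals from about 10 days to 12 months, and puts it on no common time base. Under a 'since the last visit' reading and an assumed constant rate of 0.5% to 2% per month, the month 24 percentage would be more than 20 times the week 6 percentage with no change in the device. Under a falling rate, the row could look flat or rise mildly. The direction of any distortion depends on the true rate and on the look-back, and the documents give neither. The firm conclusion is that the visits are not comparable and that the number of subjects with any deficiency is missing. No test, primary result or sample size is affected. Visits 8 and 9 are outside the six-month analysis, so the largest contrast arises only in the 24-month report.

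**What to change.** In SAP 4.11.2 and Table 14.3.3:

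1. State the look-back as it was actually asked on the CRF. Answers already collected cannot be given a new meaning.
2. Add the cumulative number and percentage of subjects with at least one device deficiency by 6 and by 24 months.
3. Add, for each between-visit interval, subjects reporting a deficiency divided by subject-months, using actual visit dates. If the CRF asked 'ever', count only first reports, among subjects not yet reported. Surgery day has no preceding interval and should stay a plain count.
4. A cumulative-incidence curve is optional. If no deficiency date is recorded, treat it as interval-censored at visit dates.

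The cost is a few sentences of SAP text and some added rows, from answers and visit dates already collected, with no new visits or burden on subjects. The downside is that few events are likely among about 52 subjects, so the interval rates will be imprecise and should be shown with their counts.
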